During the treatment period, patients who are clinically stable at an initial RECIST 1.1-defined PD may continue to receive study treatment at the discretion of the Investigator and patient. A follow-up scan is to be collected after the initial RECIST 1.1-defined PD, preferably at the next (and no later than the next) scheduled imaging visit, and no less than 4 weeks after the prior assessment of PD and this scan is evaluated using the Confirmation of Radiological Progression criteria are outlined in Appendix E. If the subsequent scan does not confirm the immediate prior radiological PD, scanning should continue until the next RECIST 1.1-defined PD which in turn will require a subsequent scan evaluated using the Confirmation of Radiological Progression criteria outlined in Appendix E.

Follow up of patients post discontinuation of study drug

Patients who have discontinued treatment due to toxicity or symptomatic deterioration, clinical progression, or who have commenced subsequent anticancer therapy will be followed up with tumor assessments until RECIST 1.1-defined PD plus an additional follow-up scan or until death (whichever comes first) and followed for survival.

Survival

All patients in the study should be followed up for survival.

Statistical methods

All statistical analyses will be performed by AstraZeneca or its representatives (e.g. CRO).

A comprehensive statistical analysis plan (SAP) will be prepared and finalized within 3 months of the first enrolled patient, and any subsequent amendments will be documented, with final amendments completed prior to reporting of the data.

All analyses will be descriptive in nature. Categorical (e.g., gender) study measures will be reported using frequency and proportions and continuous measures (e.g., age) will be reported using mean, median, standard deviation and range. Additionally, Kaplan-Meier curves will be presented for time-to-event outcomes such as overall and progression free survival.

All analyses will be based on the intention to treat (ITT) population consisted of all enrolled patients who had received at least 1 dose of study drug (chemotherapy or Durvalumab). For the overall study population and for any subpopulation, estimated 95% CIs for various event rates will be calculated.

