6.1.3 Duration of treatment and criteria for treatment through progression and for retreatment

Durvalumab will be administered beginning on Day 1 until clinical progression or RECIST 1.1-defined radiological progression (refer to 0E), unless there is unacceptable toxicity, withdrawal of consent, or another discontinuation criterion is met.

During the treatment period, patients who are clinically stable at an initial RECIST 1.1 -defined PD may continue to receive durvalumab at the discretion of the Investigator and patient as long as they are deemed to be receiving clinical benefit. A follow-up scan is to be collected after the initial RECIST 1.1 -defined PD, 4-8 weeks after the prior assessment of PD, and this follow-up scan is evaluated using the post-progression evaluation criteria outlined in 0E.

Patients with rapid tumor progression or with symptomatic progression that requires urgent medical intervention (eg, central nervous system metastasis, respiratory failure due to tumor compression, or spinal cord compression) will not be eligible for continuing durvalumab.

For all patients who are treated through progression, the Investigator should ensure that:

- The patient does not have any significant, unacceptable, or irreversible toxicities that indicate continuing treatment will not further benefit the patient. The patient may not have experienced a toxicity that required permanent discontinuation of study treatment.
- There is absence of clinical symptoms or signs indicating clinically significant disease progression accompanied by a decline in WHO/ECOG performance status to >2
- There is absence of rapid disease progression or threat to vital organs or critical anatomical sites (eg, central nervous system metastasis, respiratory failure due to tumor compression, or spinal cord compression) requiring urgent alternative medical intervention
- The patient still fulfills the eligibility criteria for this study, with the exception of inclusion criterion 8

Patients who AstraZeneca and the Investigator determine may not continue treatment after RECIST 1.1-defined PD will be followed up for survival. Patients who have discontinued treatment due to toxicity or symptomatic deterioration, or who have commenced subsequent anticancer therapy, will be followed up with tumor assessments until RECIST 1.1-defined PD plus an additional follow-up scan or until death (whichever comes first) and followed for survival.

Post final data cut off (DCO)

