PFS (days) = Date of event or Censor date – treatment start date +1

Patients who have not progressed or died at the time of analysis will be censored at the time of the latest date of assessment from their last evaluable assessment. However, if the patient progresses or dies after 2 or more missed visits, the patient will be censored at the time of the latest evaluable assessment prior to the 2 missed visits. If the patient has no evaluable visits or does not have baseline data, he/she will be censored at Day 1 unless he/she dies within 2 visits of baseline, in which case the date of death is the event date.

OS: Defined as the time from the first date of treatment until death due to any cause.

OS (days) = Death date or Censor date - treatment start date +1

Any patient not known to have died at the time of analysis will be censored based on the last recorded date on which the patient was known to be alive.

ORR: Based on Investigator–assessed response to treatment of CR and PR, per RECIST1.1.

DoR: Defined as the time from the date of first documented response per RECIST1.1 until the first date of documented progression per RECIST1.1 or death in the absence of disease progression.

DoR (days) = Date of PFS event or censoring – Date of first response +1

The end of response should coincide with the date of progression or death from any cause used for the PFS endpoint. If a patient does not progress following a response, then the patients' DoR will be censored at the PFS censoring time. DoR will not be defined for those patients who do not have a documented response.

Time to symptom deterioration (EORTC QLC-C30 and QLC-LC13): Defined as the time from start of study drug until the date of the first clinically meaningful symptom deterioration that is confirmed at the subsequent assessment or death (by any cause) in the absence of a clinically meaningful symptom deterioration, regardless of whether the patient withdraws from study drug or receives another anticancer therapy prior to symptom deterioration.

Change from baseline (EORTC QLC-C30 and QLC-LC13, PRO-CTCAE): Defined as the post-treatment value minus the value at baseline. The % change from baseline will be calculated as (postbaseline value - baseline value) / baseline value x 100.

Treatment duration: Defined as Treatment end date - Treatment start date +1; will be summarized.

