The ORR will be based on the programmatically derived RECIST 1.1 using the investigator tumor data. Summaries will be produced that present the number and percentage of patients with a tumor response (CR/PR). 95% CI will also be presented.

Duration of response

DoR will be analyzed using the investigator tumor data in responding patients. Descriptive data will be provided for the DoR in responding patients, including the associated Kaplan-Meier curves.

Overall survival

OS will be analyzed using a Kaplan-Meier plots. Summaries of the number and percentage of patients who have died, those still in survival follow-up, those lost to follow-up, and those who have withdrawn consent will be provided along with the median OS and corresponding 95% CI. In addition, the proportion of patients alive at 6, 12, and 18 months will be presented.

A subgroup analysis may be conducted comparing OS in the following subgroups, assuming sufficient sample size per subgroup: platinum therapy receiving (carboplatin or cisplatin), age, gender, performance status, smoking status and CNS metastasis at baseline (Y/N).

For each subgroup, the HR and 95% CI will be calculated by Cox regression and a log-rank test will be provided.

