#### Endpoints analyzed:

- Progression-free survival (PFS): This analysis will be performed for the Intention-to-Treat population (ITT). PFS is defined as the time from the first date of treatment until the date of objective disease progression or death (by any cause in the absence of progression) regardless of whether the patient withdraws from IP or receives another anticancer therapy prior to progression.

**PFS (days)** = Date of event or Censor date – treatment start date +1

Patients who have not progressed or died at the time of analysis will be censored at the time of the latest date of assessment from their last evaluable assessment. However, if the patient progresses or dies after 2 or more missed visits, the patient will be censored at the time of the latest evaluable assessment prior to the 2 missed visits. If the patient has no evaluable visits or does not have baseline data, he/she will be censored at Day 1 unless he/she dies within 2 visits of baseline, in which case the date of death is the event date.

The PFS analysis will be based on the programmatically derived RECIST 1.1 using the Investigator tumor assessments. It will be analysed PFS, PFS at 6 months (6mPFS) and PFS at 12 months (12mPFS).

- Objective response rate (ORR): This outcome will be analysed for the responder's analysis set. The ORR will be based on the programmatically derived RECIST 1.1 using the investigator tumor data.
- Duration of response (DoR): This outcome will be analysed for the responder's analysis set. DoR is defined as the time from the date of first documented response per RECIST1.1 until the first date of documented progression per RECIST1.1 or death in the absence of disease progression.

DoR (days) = Date of PFS event or censoring – Date of first response +1

The end of response should coincide with the date of progression or death from any cause used for the PFS endpoint. If a patient does not progress following a response, then the patients' DoR will be censored at the PFS censoring time. DoR will not be defined for those patients who do not have a documented response. It will be analysed DoR and DoR at 1 year (DoR12)

- Overall survival (OS): This analysis will be performed for the Intention-to-Treat population (ITT). OS is defined as the time from the first date of treatment until death due to any cause.

OS (days) = Death date or Censor date - treatment start date +1

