#### Endpoints analyzed:

- Progression-free survival (PFS): The PFS analysis will be based on the programmatically derived RECIST 1.1 using the Investigator tumor assessments. The analysis will be performed using Kaplan Meier plots. Summaries of the number and percentage of patients experiencing a PFS event will be provided along with median PFS and its 95% confidence interval. In addition, the proportion of patients who are progression-free at 6 (PFS 6) and 12 (PFS 12) months will be presented.

A subgroup analysis may be conducted comparing PFS in the following subgroups, assuming sufficient sample size per subgroup: platinum therapy receiving (carboplatin or cisplatin), age ( $\geq 65$ ,  $< 65$ ), gender, performance status, smoking status, CNS metastasis at baseline (Yes/No) and number of chemotherapy cycles (5 or 6 cycles vs 4 or less cycles)

For each subgroup, the HR and 95% CI will be calculated by Cox regression and a log-rank test will be provided.

- Objective response rate (ORR): The ORR will be based on the programmatically derived RECIST 1.1 using the investigator tumor data. Summaries will be produced that present the number and percentage of patients with a tumor response (CR/PR). 95% CI will also be presented.

A subgroup analysis may be conducted comparing ORR in the following subgroups, assuming sufficient sample size per subgroup: platinum therapy receiving (carboplatin or cisplatin), age ( $\geq 65$ ,  $< 65$ ), gender, performance status, smoking status, CNS metastasis at baseline (Yes/No) and number of chemotherapy cycles (5 or 6 cycles vs 4 or less cycles). Results will be compared using Chi-Squared test.

- Duration of response (DoR): DoR will be analyzed using the investigator tumor data in responding patients. Descriptive data will be provided for the DoR in responding patients (continuous data), including the associated Kaplan-Meier curves. In addition, the DoR at 1 year (DoR 12) will be analyzed.

A subgroup analysis may be conducted comparing DoR in the following subgroups, assuming sufficient sample size per subgroup: platinum therapy receiving (carboplatin

or cisplatin), age ( $\geq 65$ ,  $< 65$ ), gender, performance status, smoking status, CNS metastasis at baseline (Yes/No) and number of chemotherapy cycles (5 or 6 cycles vs 4 or less cycles)

For each subgroup, the HR and 95% CI will be calculated by Cox regression and a log-rank test will be provided.

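### ORR has no last eligible scan, so a first CR/PR after new anticancer therapy or after RECIST progression would count as a response and start a DoR

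*Protocol*

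**What the plan says.** **Response.** Protocol 9.4 bases ORR on the investigator-assessed "response to treatment of CR and PR, per RECIST1.1". SAP 4.2.2.1 adds only the source: "The ORR will be based on the programmatically derived RECIST 1.1 using the investigator tumor data". Protocol 9.5.2.2 and SAP 5.2.1 describe the output in the same words, with a 95% CI: "Summaries will be produced that present the number and percentage of patients with a tumor response (CR/PR". None of these places gives a time window, a last eligible visit or a requirement that a response be confirmed.

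**Scanning.** Protocol 6.1.3 covers patients "or who have commenced subsequent anticancer therapy, will be followed up with tumor assessments until RECIST 1.1-defined PD plus an additional follow-up scan"; scanning also ends if the patient dies. The synopsis has the same rule and adds patients who stopped for clinical progression. Protocol 7.1.1 keeps patients who stopped drug without RECIST progression on scans at least every 12 weeks. Under the synopsis and Protocol 8.1, if the scan after a first RECIST progression does not confirm it, scanning goes on to the next RECIST progression.

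**DoR.** Protocol 9.4 and SAP 4.2.2.1 start DoR at the first documented response and end it at the PFS event or PFS censoring date.

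**Later therapy elsewhere in the plan.** PFS explicitly disregards it (Protocol 9.4, SAP 4.2.2.1). Most AE summaries leave out events that follow it (Protocol 9.5.2.1). ORR has no rule in either direction.

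**The concern.** ORR and DoR are secondary endpoints meant to describe the effectiveness of durvalumab plus platinum-etoposide. Because the tumor data run past the start of other treatment, a program that searches all visits for CR or PR will pick up first responses to another regimen. That can only raise ORR. It also brings into the responders set patients whose DoR starts under a different drug.

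A second fault comes from the missing cut-off at progression. A first response recorded after RECIST progression has a start date later than its own end date, so the DoR formula breaks down.

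If the rule is left open, responder status will be settled during programming, after the data have been seen.

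**Working it through.** **1. Can the sequence arise?** Protocol 7.1 lists clinical progression and the start of alternative anticancer therapy as reasons to stop, and neither needs RECIST progression. Appendix E judges PR against the baseline sum of diameters (a fall of at least 30%). Take a baseline sum of 100 mm. A patient at 80 mm on study treatment has a 20% fall, which is SD. If new therapy brings the sum to 70 mm, the fall is 30% and the visit is PR. One such visit is enough.

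**2. Who is exposed?** Only patients with no earlier CR or PR who either (a) start new therapy before RECIST progression, or (b) are scanned after RECIST progression. Group (b) may still be on durvalumab, since Protocol 6.1.3 allows treatment through progression. For them the problem is the DoR formula more than attribution.

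**3. DoR after progression.** The formula is date of PFS event − date of first response + 1. If the first response comes d days after the progression date, DoR = −d + 1. With d = 1 this is 0. With d = 28 (the follow-up scan is due no sooner than 4 weeks after progression) it is −27 days.

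**4. The plan's own precision figures.** Protocol 9.2 gives exact 95% intervals at n=85 for adverse-event rates and none for ORR. Clopper-Pearson limits reproduce them:
- 17/85: 12.1–30.1
- 21/85: 16.0–35.3
- 51/85: 48.8–70.5
- 60/85: 59.7–80.0

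**5. Size of the ORR effect.** This takes the safety analysis set as denominator (Protocol 9.3) and n=85.
- Per patient: 1/85 = 1.18 points.
- Let q be the share of patients exposed and r the share of those who then reach CR or PR. The documents give neither, so both are assumptions. Expected extra responders = 85 × q × r, and the shift in ORR = 100 × q × r points.
- Low end, q = 2%, r = 10%: 0.17 patients, 0.2 points.
- Middle, q = 5%, r = 20%: 0.85 patients, 1.0 point.
- High end, q = 10%, r = 30%: 2.55 patients, 3.0 points.
- Illustration: 51/85 = 60.0% (48.8–70.5). With two extra responders, 53/85 = 62.4% (51.2–72.6).

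**6. Subgroups.** SAP 5.2.1 may compare ORR by performance status with a chi-squared test. PS 2 is capped at 30% of patients: 0.30 × 85 = 25.5, so at most 25. One such response there moves ORR by 1/25 = 4.0 points.

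**7. Denominator.** Protocol 9.3 assigns ORR to the safety analysis set. SAP 4.2.2.1 assigns it to the responders set, where every patient has a response and ORR is 100% by construction. The figures in steps 5 and 6 hold only under the protocol's set.

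**The case against.** The best counter-argument is that the plan already implies a limit. Protocol 9.4 speaks of response to treatment, Section 6 defines study treatment as platinum, etoposide and durvalumab, and Section 8.1 describes follow-up images as collected during study treatment. Appendix E also limits visits after an intervention on a target lesion to not evaluable or PD, with an open-ended list of interventions outside study treatment.

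This stands in part. A reader might infer that the plan credits second-line responses to durvalumab plus platinum-etoposide. The documents do not say so, and the wording just cited suggests the opposite intent. But none of it is a derivation rule. The SAP's ORR text drops the reference to treatment, the follow-up sections require scans well beyond study treatment, and the interventions that Appendix E names are local procedures. It does not tell sites to apply that rule to new systemic therapy.

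A reader might also size the problem from the 9.4% rate of AEs leading to discontinuation that Protocol 2.3.2.2 quotes from CASPIAN: 0.094 × 85 = 8.0 patients, and 1.2 to 3.5 points if 1 to 3 of them respond later. That is the wrong group. If the response rate of up to 70% quoted in the Introduction applied (an assumption), only 8 × 0.30 = 2.4 of them would lack an earlier response. They would still have to start new therapy before RECIST progression and then respond. Patients who stop for clinical progression add to the pool, but the documents do not quantify them.

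Finally, ORR is descriptive and secondary in a single-arm study with no hypothesis, and the exact interval is about ±10 to 11 points at rates of 60–70%. That limits the importance of the point but does not remove it.

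**Conclusion.** The point holds as a gap in the derivation of ORR and of entry into DoR. Literal execution would count a first CR or PR on later therapy. It would also give a zero or negative DoR when the first CR or PR follows RECIST progression. The direction on ORR is upward. The size is probably small: 1.2 points per patient at n=85, and 0.2 to 3.0 points overall under the assumed 2–10% exposed and 10–30% responding. A subgroup as small as PS 2 is more sensitive. The documents give no count of exposed patients, so no single corrected ORR can be stated.

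**What to change.** In Protocol 9.4 and 9.5.2.2 and SAP 4.2.2.1 and 5.2.1, define a responder as a patient with CR or PR recorded on or before first RECIST progression and before the start of any subsequent anticancer therapy. Keep every other patient in the safety analysis set in the denominator as a non-responder. This requires changing the ORR population in SAP 4.2.2.1 from the responders set to the set in Protocol 9.3. Apply the same definition to entry into the DoR analysis.

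Leave PFS as written, and with it the end of DoR. DoR in true responders may then still run into later therapy, because PFS disregards it, and the report should say so.

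The change affects the analysis only. It needs no new data, since the start date of subsequent therapy is already collected (Protocol Table 2, footnote c). The cost is a sentence in each document and the population correction. The reported ORR may be slightly lower, and a first response seen only after RECIST progression, including one on continued durvalumab, would no longer count.

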9.5.2.3 Patient reported outcomes

Summary measures of visit and overall compliance and completion rates will be derived for each PRO questionnaire. Refer to the SAP for details.

For PRO symptoms and health related quality of life endpoints, the main concepts of interest have been identified using a literature review, and detailed qualitative interviews SCLC patient and clinicians. The key symptoms were: cough, hemoptysis, dyspnea, chest pain, insomnia, fatigue and appetite loss.

Therefore we would like to pre-specify that an effective treatment would reduce time to deterioration and effect mean change from baseline in these key SCLC symptoms. The prespecified symptomatic endpoints are as follows: time to deterioration from baseline of cough, hemoptysis, dyspnea and chest pain from EORTC QLQ- LC13; and insomnia, fatigue and appetite loss from EORTC QLQ -C30; as well as average mean change of the key symptoms.

In addition, physical functioning and overall health status domains of the EORTC QLQ-C30 are furthermore pre-specified endpoints of interest.

The detail how this data will be analysed and the effect we would like to see to determine a symptomatic treatment effect will further be detailed and pre-specified in the SAP.

(a) EORTC QLQ-C30

If possible, time to symptom deterioration will be summarized for each of the 3 symptom scales (fatigue, pain, nausea/vomiting) and the 5 individual symptom items (dyspnea, insomnia, appetite loss, constipation, diarrhea). Similarly, a summary of QoL/function deterioration will be summarized for each of the function scales (physical, role, emotional, cognitive, and social) and global health status/QoL. This will be achieved by using Kaplan-Meier product limit methods to provide summaries of the number and percentage of patients experiencing a clinically meaningful deterioration or death, the median time to deterioration together with the corresponding 95% CIs, as well as the Kaplan-Meier plots.

Summaries of original and change from baseline values of each symptom scale/item, the global HRQoL score, and each functional domain will be reported by visit. Details will provided in the SAP.

Definition of clinically meaningful changes

Changes in score compared with baseline will be evaluated. A minimum clinically meaningful change is defined as an absolute change in the score from baseline of ≥ 10 points for scales/items from the EORTC QLQ-C30 (Osoba et al 1998). For example, a clinically meaningful improvement in physical function (as assessed by EORTC QLQ-C30) is defined as an increase in the score from baseline of ≥ 10 points, whereas a clinically meaningful deterioration is defined as a decrease in the score from baseline of ≥ 10 points. At each post-baseline assessment, the change in symptoms/functioning from baseline will be categorised as improvement, no change, or deterioration as shown in Table 15.

Table 14. Mean change and visit response in health related quality of life

Score	Change from Baseline (points)	Visit Response
EORTC QLQ-C30 Global quality of life score	$\geq +10$	Improvement
	≤ -10	Deterioration
	Otherwise	No Change
EORTC QLQ-C30 symptom scales/items	$\geq +10$	Improvement
	≤ -10	Deterioration
	Otherwise	No Change
EORTC QLQ-C30 functional scales	$\geq +10$	Improvement
	≤ -10	Deterioration
	Otherwise	No Change

EORTC QLQ-C30 = European Organisation for Research and Treatment of Cancer 30-item core quality of life questionnaire.

For each subscale, if < 50% of the subscale items are missing, then the subscale score will be divided by the number of nonmissing items and multiplied by the total number of items on the subscales (Fairman et al 2014). If at least 50% of the items are missing, then that subscale will be treated as missing. Missing single items are treated as missing. The reason for any missing questionnaire will be identified and recorded. If there is evidence that the missing data are systematic, missing values will be handled to ensure that any possible bias is minimized.

Time to symptom deterioration

For each of the symptoms scales/items in the EORTC QLQ-C30 questionnaire, time to symptom deterioration will be defined as the time from start of study drug until the date of the first clinically meaningful symptom deterioration (an increase in the score from baseline of ≥ 10 points) that is confirmed at the subsequent assessment (at least 14 days apart) or death (by any cause) in the absence of a clinically meaningful symptom deterioration, regardless of whether the patient withdraws from study drug or receives another anticancer therapy prior to symptom deterioration. Death will be included as an event only if the death occurs within 2 visits of the last PRO assessment where the symptom change could be evaluated.

Patients with a single deterioration and no further assessments will be treated as deteriorated in the analysis. Patients whose symptoms (as measured by EORTC QLQ-C30) have not shown a clinically meaningful deterioration and who are alive at the time of the analysis will be censored at the time of their last PRO assessment where the symptom could be evaluated. Also, if symptoms deteriorate after 2 or more missed PRO assessment visits or the patient dies after 2 or more missed PRO

assessment visits, the patient will be censored at the time of the last PRO assessment where the symptom could be evaluated. If a patient has no evaluable visits or does not have baseline data, he/she will be censored at Day 1.

The analysis of time to symptom deterioration will be done with a subset of patients who have baseline scores of ≤ 90 .

Time to quality of life/function deterioration

For QoL, time to deterioration will be defined as the time from start of study drug until the date of the first clinically meaningful deterioration (a decrease in the function scales or the global health status/QoL from baseline of ≥ 10 points) that is confirmed at the subsequent assessment (at least 14 days apart) or death (by any cause) in the absence of a clinically meaningful deterioration, regardless of whether the patient withdraws from study drug or receives another anticancer therapy prior to QoL/function deterioration. Death will be included as an event only if the death occurs within 2 visits of the last PRO assessment where the QoL/function change could be evaluated.

Patients whose QoL (as measured by EORTC QLQ-C30) have not shown a clinically meaningful deterioration and who are alive at the time of the analysis will be censored at the time of their last PRO assessment where the QoL/function could be evaluated. Also, if QoL deteriorates after 2 or more missed PRO assessment visits or the patient dies after 2 or more missed PRO assessment visits, the patient will be censored at the time of the last PRO assessment where QoL/function could be evaluated. If a patient has no evaluable visits or does not have baseline data, he/she will be censored at Day 1.

Symptom improvement rate

The symptom improvement rate will be defined as the number (%) of patients with 2 consecutive assessments at least 14 days apart that show a clinically meaningful improvement (a decrease from baseline score ≥ 10 points for EORTC QLQ-C30 symptom scales/items) in that symptom from baseline.

Quality of life/function improvement rate

The QoL/function improvement rate will be defined as the number (%) of patients with 2 consecutive assessments at least 14 days apart that show a clinically meaningful improvement (an increase from baseline score ≥ 10 points for EORTC QLQ-C30 functional scales and global health status/QoL) in that scale from baseline.

(b) EORTC QLQ-LC13

Data will be summarized for each of the symptom items in EORTC QLQ-LC13 as outlined above for EORTC QLQ-C30.

Summaries of original and change from baseline values of each symptom (dyspnea, cough, hemoptysis, chest pain, arm/shoulder pain, and other pain) and each treatment-related side effect (sore mouth, dysphagia, peripheral neuropathy, and alopecia) will be reported by visit. Details will be provided in the SAP.

(c) **PRO-CTCAE**

PRO-CTCAE data will be presented using summaries and descriptive statistics. Further details will be provided in the SAP.

